introduce the study and ask if they are interested in learning more. If the patient agrees and would like more information about the study, the nephrologist/nurse practitioner will ask them to sign a DaVita “HIPAA Authorization to Use and Disclose Information for Research Purposes” form so their information may be shared with our study team and we can provide them with more information about the study. DaVita will provide the Program Manager with a list of eligible potential participants with signed DaVita HIPAA authorization forms. Our research team will contact patients on the list either by phone or in-person to discuss the study and if they are interested and agree to participate, they will provide informed consent and enrolled.

Participants will be enrolled at 4 locations in New York City: The Lower Manhattan Dialysis Center 1, The Lower Manhattan Dialysis Center 2, River Renal Services, Inc. and Chinatown Dialysis Center, LLC. The NYU Langone Health study team will analyze and collect data for this study.

Timeline: We will administer the interventions in two waves. In wave 2 (2 years after the start of the study), we will return to the dialysis centers in the first wave and begin enrollment again. This will allow us to identify new HD patients at each center. We will allow 1 month for identification of participants, initial contact by a research assistant, and baseline assessment as described below. Participants will be followed for 1 year after the end of the intervention for mortality and hospitalization.

Randomization:

We will randomize participants after completion of the baseline assessments. Participants will be block randomized (i.e., stratified over time) and stratified by sex, race/ethnicity, and dialysis center. They will be randomly assigned to one of the four study arms using a blind and secure computer based allocation system: **a) 6 months of CT alone, b) 6 months of ET alone, c) 6 months of CT+ET, d) standard of care.** We will use block sizes of four to ensure desired sizes in each arm. Given the nature of our interventions, it is not possible to blind the participant, treating provider and other HD center staff.

Intradialytic Interventions to Preserve Executive Function:

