Other patient-centered outcomes	Validated self-report instrument	PROMIS-29 short-form profile: anxiety, depression, fatigue, pain, perceived function, sleep disturbance, and participation in social roles/activities, ability to return to work	Baseline and at 3- and 6-month Follow-up
Demographics*	Self-report and abstraction	Age, sex, race/ethnicity, and education	Baseline
Health behaviors	Self-report and abstraction	Smoking status, alcohol intake, illicit drug use	Baseline and at 3- and 6-month follow up
Medical factors	Chart abstraction	History of chronic and infectious diseases	Baseline and at 3- and 6-month follow up
Clinical measures	Chart abstraction	BMI, eGFR, blood pressure, cholesterol	Baseline and at 3- and 6-month Follow-up
Dialysis factors	Chart abstraction	Time on dialysis, access site, schedule, cause of ESRD	Baseline and at 3- and 6-month Follow-up
DSMB Review	Direct observation	Falls during intervention or assessment, hypotension, hypertension, elevated heart rate	At every dialysis session
	Self-report	Cramping and headache	At every dialysis session
	Self-report	Injurious falls	Baseline and at 3- and 6-month Follow-up

All measures of executive function, global cognitive function, frailty, and the SPPB (walk speed, chair stands and balance) will be assessed in-person prior to the start of the dialysis session.

Assessment of Executive Function:

- *Trail Making Test A and B (TMTA and TMTB)* scores are validated measures of executive function (i.e., cognitive shifting, cognitive flexibility), attention, concentration, and psychomotor speed (5). These tests measure the time required to connect a series of sequentially numbered (TMTA) and numbered/lettered (TMTB) circles. Needing more time to complete the tests indicates worse executive function; times are capped at 3 minutes for TMTA and 5 minutes for TMTB.
- The *Stroop Test* (reading, color-naming, and interference sub-tasks) (103) evaluates the inhibitory control of executive function and involves reading the name of a color printed in a different color ink: **BLUE**. The time ratio of color-word interference and color-only tasks will be calculated.

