Follow-up Assessments: We will perform follow-up assessments at 3 months of intervention and 6 months of intervention (measures listed in Table 2) in the dialysis center using a similar approach to the baseline assessment for comparability of the measures. Research assistants blinded to the assigned study arm will perform follow up assessments.

The Principal Investigator/ Program Manager will inform the appropriate dialysis center treating nephrologist/nurse practitioner of any abnormal findings for cognitive function, anxiety, and depression at the 3 month and 6 month assessments.

Data collection for variables needed for DSMB review. Falls during the intervention or assessment will be directly observed by study staff at each intervention session throughout the whole study. Hypotension (SBP<110 mmHg or DBP<50 mmHg) and hypertension (SBP>150 mmHg or DBP>90 mmHg) will be identified during the clinical measurements of blood pressure that occur approximately 10 times throughout the dialysis session. Similarly elevated heart rate (>80% of maximum heart rate calculated as 220-participant age will be identified during the clinical measurements of heart rate that occur approximately 10 times throughout the dialysis session. Cramping and headaches will be noted if a participant tells the study staff that they are experiencing these events. Injurious falls for DSMB review outside of the dialysis session will be self-reported by participants as part of the questionnaire at 3- and 6-months follow-up.

Plan for Fidelity Monitoring. In the pilot study, there was a small dropout rate (3/23), which is consistent with other intradialytic exercise interventions at 6 months (86) and there is high compliance (88%) with ET (63). We will allow for temporary noncompliance due to acute illness or travel. We will add additional sessions onto the end of the intervention period (no more than 2 weeks) in any of the study arms, as has previously been proposed in intradialytic intervention trials (86). The Program Manager/Study Coordinator

will visit the dialysis centers administering these arms of the study monthly throughout the course of the intervention to give a refresher on the safe and effective use of the foot peddlers. The PI or project manager will visit each clinic weekly during the administration of the intervention to directly observe compliance and facilitate communication among the HD clinic staff, patients, and study staff. Research assistants will record the:

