2.1. Time to Event Outcomes: Mortality. To examine the univariate association between study arm and mortality, separate product-limit estimated cumulative incidence curves will be calculated. Next, we will use a Cox proportional hazards model to estimate the association of study arm with time to the development of mortality. Censoring will occur at loss to follow-up or KT. The hazard function for the Cox model is:

$$\lambda(t|X_i) = \lambda_0(t) \exp(X_i \beta)$$

where x_i is the value of the covariate X for the i th participant, and $\lambda_0(t)$ is the baseline hazard function. If the proportional hazards assumption is not met, we will include an interaction with time.

2.2. Dichotomous Outcomes: Poor Lower Extremity Function, poor HRQOL, return to work, and amputation. We will test whether the study arm is associated with poor lower extremity function, poor HRQOL, return to work, and amputation using logistic regression or a modified Poisson regression (145), if the outcome is $>10\%$.

2.3. Count Outcomes: Number of Falls and Hospitalizations. We will use Poisson regression to test whether the study arm is associated with the number of falls and hospitalizations within the 3 months of the intervention.

3.0. Analytic Methods: Effect of CT, ET, and CT+ET on patient-centered outcomes.

Change in Patient-centered Outcome: For each patient-centered outcome, we will calculate a score. We will treat each patient-centered outcome as continuous and will estimate the change in these outcomes between baseline and 3 months. We will analyze each patient-centered outcome separately. We will analyze the change in these outcomes using the analytic plan described in 1.0.

3.1. Change in Patient-centered Outcome over 6 Months. Patient-centered outcomes are longitudinal data (3 and 6 months) and analyzed using the analytic plan described in 2.0 for repeated measures of executive function.

4.0. Treatment Effect Heterogeneity. Frailty has been associated with worse trajectories of executive function in older adults (146) and HD patients (16). Therefore, we will explore treatment heterogeneity between those who are frail and nonfrail in all primary and secondary outcomes. We will include an interaction term between frailty status and intervention type (study arm) to assess difference in treatment effect by frailty status. Using a similar approach, we will test for treatment effect heterogeneity by age, sex, and race/ethnicity.

Risks:

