We will keep all data collected strictly confidential so there is minimal risk of loss of confidentiality. All participating faculty and staff have received appropriate training in the responsible conduct of research, protection of human subject participants, and HIPAA regulations. All data collection instruments and consent forms will be kept in a locked cabinet. All questionnaires, assessments and cognitive function data will be stored in RedCap, a secured database. To maximize confidentiality, only the study investigators, data manager and key study personnel will have access to the information.

Data Safety Monitoring Board (DSMB) and Adverse Event Reporting:

An independent DSMB will be established to oversee the safety and progress of this trial, comprised of five individuals (a patient advocate, an ethicist, a statistician, a nephrologist, and a research nurse) who will serve in this capacity throughout the entirety of the trial. We will ensure that all members of the DSMB disclose of any conflicts of interest. The DSMB will have pertinent experience and review accumulating data from this RCT on a regular basis with the goal of enhancing the safety of the trial participants. A DSMB is warranted in this RCT because the study is being performed in a potentially vulnerable population, namely those with ESRD on HD and this population is at elevated risk of serious outcomes. A medical monitor will be included on the DSMB to review all events and determine whether they classify as AE's/ or SAE's.

We will monitor the number of injurious falls resulting in a medical encounter during the 6 months of interventions. This data will be obtained during the survey portion of our assessments by asking the participant to self-report the number of falls in the last 6 months. Additionally, falls during the intervention or assessment will be directly observed and recorded by study staff. Any falls will be reported to the medical monitor for review and determination whether they classify as an AE or SAE attributable to the interventions.

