The DSMB will be identified and managed through the ICTR and will be established and operated using the Guidance put forth by the US Food and Drug Administration "Guidance for Clinical Trial Sponsors: Establishment and Operation of Clinical Trial Data Monitoring Committees" (<https://www.fda.gov/downloads/RegulatoryInformation/Guidances/ucm127073.pdf>). The DSMB will be local and managed by the ICTR to allow for quick convening of meetings in the event of an unexpected result that raises concerns.

None of these individuals will be involved in the design or conduct of the trial. Any unanticipated problem or adverse event will be reported as outlined in JHU IRB policy 103.6(b). When possible the DSMB will be blinded to the study arm.

If any SAEs are more common in one of the three intervention arms compared to the standard of care arm, then the DSMB will consider termination of the study if the risks outweigh the benefits for participants. All SAEs that are deemed to have a causal relationship with the interventions in one of the arms of the study will be reviewed by the DSMB for the consideration of patient safety.

Planned DSMB Reviews:

The Data and Safety Monitoring Board (DSMB) shall review safety data during planned DSMB Data Review Meetings when 10%, 25%, and 50% of enrolled participants have completed 3 months of interventions and to analyze and review the interim analyses of these adverse events during active data collection. Data for the planned safety reviews will include, at a minimum, a listing of all reported AEs and SAEs. The DSMB will be informed of an Expedited Safety Report in a timely manner. The DSMB will have a final meeting at the end of the study.

We have performed a comprehensive literature search of published and unpublished manuscripts to identify possible side effects, adverse events, and serious adverse events of CT and ET interventions. No adverse events were noted in the literature search for side effects, adverse events or serious adverse events for CT. We theorize that the two most common risks associated with CT are the following: 1) boredom 2) frustration and 3) headache.

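### Staff watch for falls in the dialysis unit at every intervention session in three arms but only at assessments in standard of care, and the all-arm falls survey is inconsistent in scope and look-back.

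*Combined protocol and SAP*

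**What the plan says.** The DSMB and Adverse Event Reporting section sets the contrast. The board considers termination, weighing risk against benefit, "If any SAEs are more common in one of the three intervention arms compared to the standard of care arm". Falls feed that count: "Any falls will be reported to the medical monitor for review and determination whether they classify as an AE or SAE".

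Falls reach the study by two routes.

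- **Staff observation.** The paragraph on data collection for DSMB review says: "Falls during the intervention or assessment will be directly observed by study staff at each intervention session throughout the whole study". The DSMB Review row of Table 2 gives the timing as every dialysis session, but the event it lists is "Falls during intervention or assessment, hypotension, hypertension, elevated heart rate". The DSMB section keeps the same restriction.
- **Self-report in all arms.** The data-collection paragraph says: "Injurious falls for DSMB review outside of the dialysis session will be self-reported by participants", at 3 and 6 months. The DSMB section describes injurious falls with a medical encounter as obtained "by asking the participant to self-report the number of falls in the last 6 months", with no limit on where the fall happened. Table 2 also sets no such limit and schedules the item at baseline, 3 and 6 months.

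Section 2.3 then makes falls a trial outcome. Poisson regression tests whether "study arm is associated with the number of falls and hospitalizations within the 3 months of the intervention". It names no source for the fall count.

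**The concern.** The SC arm has no intervention sessions. The plan therefore looks for falls in the unit more often in the arms being tested than in the arm they are compared with. A fall seen by a research assistant in an intervention arm enters the record. A similar fall in an SC participant on an ordinary dialysis day enters only if the survey picks it up, and the plan is unclear whether the survey covers falls in the unit.

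Two comparisons depend on this: the DSMB's comparison of SAEs with SC, and the section 2.3 comparison of falls. The second has a further problem, because a 6-month recall question does not fit a 3-month outcome. The DSMB could allow for unequal capture if it knew how each fall was found, but the plan does not call for falls to be shown by source.

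**Working it through.** The plan gives no fall rate, SAE rate or operating characteristic for this trigger, so there is no stated figure to reproduce. The check sets the sections side by side, then sizes what can be sized.

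**1. Which route covers which fall**

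| Fall | CT, ET, CT+ET | SC |
|---|---|---|
| In the unit, during an intervention session | Staff observation | No such session |
| In the unit, at an assessment | Staff observation | Staff observation |
| In the unit, at any other time | Survey, if it covers the unit | Survey, if it covers the unit |
| Outside the dialysis session | Survey | Survey |

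The every-session timing in Table 2 does not extend observation to routine SC sessions, because the listed event still requires an intervention or an assessment.

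**2. How often staff observe**

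Inputs: dialysis 2–3 times weekly (Study Population), 6 months of intervention, and the 88% exercise compliance cited under Plan for Fidelity Monitoring.

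- By month 3: 13 × 3 = 39 sessions (13 × 2 = 26). At 88% this is 39 × 0.88 = 34.3 (26 × 0.88 = 22.9).
- By month 6: 26 × 3 = 78 sessions (26 × 2 = 52).
- Follow-up assessments in every arm: one by month 3, two by month 6.

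These counts show that the routes differ. They do not measure how many SC falls are missed.

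**3. Look-back**

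Assume a constant fall rate, equal arms before randomisation, and a true ratio R afterwards. A 6-month question at month 3 covers about 3 months before and 3 months after randomisation, so

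observed ratio = (3 × 1 + 3 × R) / 6.

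- R = 2: (3 + 6) / 6 = 1.5.
- R = 0.5: (3 + 1.5) / 6 = 0.75.

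The comparison moves toward 1 whichever way the true effect lies.

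**4. Effect on the SAE comparison, by assumption only**

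Let s be the share of an intervention arm's recorded SAEs that are falls in the unit that would have been missed in SC. With no true harm, the expected ratio is 1 / (1 − s).

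| Assumed s | Expected ratio |
|---|---|
| 0.02 | 1.02 |
| 0.05 | 1.05 |
| 0.10 | 1.11 |

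Nothing in the documents fixes s. To see what this does to the trigger, assume independent Poisson counts with 5 SAEs expected per intervention arm and 5(1 − s) in SC. The chance that at least one intervention arm exceeds SC is 0.692 with equal capture, and 0.705, 0.724 and 0.755 at s = 0.02, 0.05 and 0.10.

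**5. Cramping and headache**

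Table 2 schedules these at every dialysis session. The data-collection paragraph, however, records them only when the participant mentions them to study staff. Research assistants are on site to run and monitor the intervention arms, so opportunities to mention a symptom may differ by arm. Blood pressure and heart rate come from routine clinical readings and do not share this weakness.

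**The case against.** The strongest reply is that the survey covers every arm, and a fall serious enough to be an SAE should usually be recalled. This stands, and it is why the effect on SAEs is judged modest. A reader might infer that SC falls in the unit are never captured. The documents do not support that: the DSMB section and Table 2 place no location limit on self-report. Only the data-collection paragraph does.

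A second reply is that the session counts are not extra capture. Observation is tied to blocks of about 30 minutes with a tablet or a pedaller at the dialysis chair. A fall then may be a real effect of the intervention rather than a background fall that SC also has. This stands. Reading 78 sessions against none as the size of the bias would be wrong.

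Third, the trigger is a judgement and not an automatic stop. The DSMB receives a listing of reported AEs and SAEs, and adverse events are reported under IRB policy with no arm limit stated. For safety, finding more harm in the active arms is the cautious direction. This also stands, and it argues against removing staff-observed falls from the safety comparison. In the illustration above, the lack of a numerical threshold matters more than unequal capture: chance alone gives 0.692.

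Fourth, the 6-month wording fits the month-6 survey, and the plan does not say that it is used unchanged at month 3. The dilution is therefore conditional. But the same survey runs at month 3, and section 2.3 needs a 3-month count, so the plan should say which window applies.

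Finally, the updated statistical methods attribute termination to COVID-19 restrictions and name no falls comparison. Nothing suggests that this trigger ended the trial, and a falls result may not be reported.

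**Conclusion.** The point holds as a modest one, worth considering. Planned observation of falls in the unit is unequal between the intervention arms and SC. The survey that should even this out is described inconsistently on place, and its stated look-back does not fit the 3-month outcome.

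The size is unknown, because the documents give no fall or SAE rates; the ratios 1.02 to 1.11 rest entirely on assumed shares. For SAEs the effect is probably modest. For section 2.3 it depends on whether staff-observed falls are counted and which look-back is used. The figure of 1.5 for a true ratio of 2 assumes a constant rate and a 6-month question at month 3.

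A reader might infer that the net direction of bias is known. It is not. Staff observation can only add captured falls to the intervention arms, while the look-back pulls toward 1. A reader might also infer from Table 2 that cramping and headache are free of the problem. They should not be described as exempt, since they depend on what participants tell study staff.

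**What to change.** 1. In all four arms, ask at 3 and 6 months about falls since the last assessment, in or outside the dialysis unit, and whether each led to a medical encounter. Use this wording in both the data-collection paragraph and the DSMB section.
2. Base the section 2.3 falls comparison on that all-arm source.
3. Give the DSMB fall AEs and SAEs by arm and by source (survey, or staff observation at an intervention session). Keep every fall in the safety listing and every serious in-session fall in the SAE comparison.

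A falls field in the chart abstraction already planned at 3 and 6 months is optional. It helps only if centre records log falls, which the documents do not say.

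Because the trial has been terminated, the practical step is to state the look-back that was used and to tabulate any reported falls by source.

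The cost is one reworded survey item and one extra table column, with no new visits.

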Risk from Cognitive Training Intervention:

Participants in the CT arm may feel tired or bored from playing similar cognitive games. They may feel frustrated if they are trying to learn new games and are unsuccessful with the games. Participants may develop a headache due to eyestrain from focusing on the tablet screen. All participants will be encouraged to wear their reading glasses while performing the CT if applicable.

Risk from Exercise Training Intervention:

Participants in the ET arm may experience fatigue, exhaustion, discomfort, muscle soreness, pain or cramping in the legs from using the foot peddler. Participants may experience shortness of breath, a change in heart rate or blood pressure while performing the activity.

Risk from Frailty Measurements and Physical Function Assessments:

Participants may experience fatigue or exhaustion from performing the grip strength, chair stands, balance and walk speed.

Risk from Quality of Life and Health Questionnaires:

Participants may experience fatigue, exhaustion, emotional discomfort or boredom from answering the questionnaires.

Minimization of Risks:

All participants will go through an eligibility screening process. We will enroll only those who meet all of the inclusion criteria and none of the exclusion criteria. The treating nephrologist is required to give permission for a patient to enroll in the study to ensure it is safe for them to participate.

All participants will sign an IRB-approved informed consent. We will inform them that participation is strictly voluntary and that they may decline to continue participation in the study at any time point, discontinue the assessments during the session, or refuse to answer any questions they do not want to. At the start of each session, we will inform the participants in the CT, ET, and CT+ ET arms that they are free to stop the activity at any time if they feel any discomfort or for some other reason cannot continue. Additionally, physicians, nurse practitioners, and dialysis staff will be on staff during the session to help monitor the participants health while undergoing hemodialysis and participating in the study.

The study team will make every effort to protect the participants' privacy by conducting interviews and assessments in an area at the dialysis center that is not within earshot or view of other clinic patients.

Confidentiality and Risk Protection:

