There are greater risks associated with the ET intervention than with the CT intervention. The main risks associated with ET include: 1) Hypotension or low blood pressure which can cause dizziness and fainting. Hypotension can frequently occur during hemodialysis due to fluid removal. Hypotension is the most common risk of intradialytic ET and can occur in up to 33% of dialysis sessions in which exercise is involved, 2) cramping, muscle soreness, pain and fatigue, and 3) dyspnea or shortness of breath which occurs commonly during exercise. While hypertension and elevated heart rate were not noted as a risk associated with ET, we will also consider hypertension as a possible risk. Blood pressure reading of SBP>150 or DBP>90 mmHg will be considered as hypertension. SBP<110 or DBP<50 mmHg will be considered as hypotension. Heart rate that is consistently >80% of maximum heart rate will be considered as elevated.

Ad Hoc DSMB Reviews

In addition to the pre-scheduled data reviews and planned safety monitoring, the DSMB may be called upon for ad hoc reviews. The DSMB will review any event that potentially impacts safety at the request of the PI or NIDDK representative. In addition, the following events will trigger an ad hoc comprehensive DSMB Safety Review:

- Any death in the study which is considered possibly or definitely related to a study procedure.
- If any of the following adverse events occur at a significant higher rate than expected in the CT, ET, or CT+ET arm: muscle cramping, hypotension, or headache. We have outlined thresholds for pausing rules for rates of cramping, hypotension, hypertension, elevated heart rate, or headache which will trigger a mandatory pause in study enrollment for an unscheduled Data Safety and Monitoring Board review.

Cramping/Muscle Soreness: At the first day of each month, we will perform a Bayesian analysis of the ratio of cramping rates between ET arm (or CT+ET arm) versus the SC group. We will use a prior distribution of beta for each subgroup. We will then analyze the ratio of the distributions using a Monte

Carlo simulation. If there is 75% chance that [rate of cramping in the ET arm or CT+ET arm] divided by [rate of cramping in the SC arm] exceeds 1.10 (10% more in ET arm or CT+ET arm), we will pause the study pending DSMB recommendation.

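### Shortness of breath is named as a main exercise risk but is not an every-session DSMB item, so its rate cannot be compared between arms on systematically collected data

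*Combined protocol and SAP*

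**What the plan says.** The protocol names shortness of breath as an ET risk twice. Under Planned DSMB Reviews, three groups of main ET risks are listed: hypotension; cramping with soreness, pain and fatigue; and "3) dyspnea or shortness of breath which occurs commonly during exercise". The section Risk from Exercise Training Intervention says: "Participants may experience shortness of breath, a change in heart rate or blood pressure while performing the activity".

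Table 2 has DSMB Review rows collected at every dialysis session. The directly observed row reads "Falls during intervention or assessment, hypotension, hypertension, elevated heart rate"; the self-report row reads "Cramping and headache". A third row covers injurious falls, self-reported at the assessment visits. The paragraph on data collection for DSMB review (under Follow-up Assessments) works through the same events and says of the symptoms: "Cramping and headaches will be noted if a participant tells the study staff that they are experiencing these events".

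The Ad Hoc DSMB Reviews section then says: "We have outlined thresholds for pausing rules for rates of cramping, hypotension, hypertension, elevated heart rate, or headache". Each of these five events has a comparison of intervention arms with standard of care (SC). Dyspnea is in neither the data collection lists nor these rules.

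On two of the events that are collected, the protocol says: "While hypertension and elevated heart rate were not noted as a risk associated with ET, we will also consider hypertension as a possible risk".

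**The concern.** A safety board sees an excess of a common, non-serious symptom by comparing rates that were collected in the same way in every arm. The plan takes that approach for hypotension and cramping, and extends it as a precaution to hypertension and elevated heart rate. It gives no reason for leaving out a symptom that it ranks among the main ET risks and describes as common.

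If the plan is followed exactly, dyspnea appears only when someone chooses to report it. Such reports have no session denominator and no matched SC record. At stake is whether the DSMB, and later the reader of the safety results, can judge how much breathlessness the ET and combined CT+ET arms added to ordinary dialysis. A short list of cases could be taken as reassurance when the plan never scheduled anyone to record the symptom.

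**Working it through.** No formula applies to the main point, so the risk lists and the collection lists are set side by side.

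| Event | Named as an ET risk | Every-session item in Table 2 | In the DSMB data collection paragraph | Between-arm pausing rule |
|---|---|---|---|---|
| Hypotension | Main risk 1 | Yes, observed | Yes | Yes |
| Cramping | Main risk 2 | Yes, self-report | Yes | Yes |
| Soreness, pain, fatigue | Main risk 2 | No | No | Soreness only, in the title of the cramping rule |
| Dyspnea | Main risk 3, and under Risk from Exercise Training Intervention | No | No | No |
| Hypertension | Not noted in the literature search; blood pressure change listed under Risk from Exercise Training Intervention | Yes, observed | Yes | Yes |
| Elevated heart rate | Not noted in the literature search; heart rate change listed under Risk from Exercise Training Intervention | Yes, observed | Yes | Yes |

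Reading across:

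1. Main risks 1 and 2 each have at least one component with scheduled per-session collection and a between-arm rule. Main risk 3 has neither.
2. Pain and fatigue, though not session items, are PROMIS-29 domains in Table 2 at baseline, 3 and 6 months. Table 2 names no dyspnea item at any visit.
3. The other routes to the DSMB are general. Research assistants record safety concerns and pass them to the principal investigator (Intradialytic Interventions section). A medical monitor on the DSMB classifies events (DSMB and Adverse Event Reporting). The planned reviews receive at least the adverse events that were reported (Planned DSMB Reviews). None of these schedules a dyspnea record or supplies a count of sessions at which it was looked for.

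Scope, at planned size:

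- Participants assigned to exercise: 200 planned x 2 of 4 arms = 100.
- Sessions per participant: six months taken as 26 weeks, at the 2 to 3 sessions a week in Study Population, gives 26 x 2 = 52 to 26 x 3 = 78.
- Sessions in the two exercising arms: 100 x 52 = 5,200 to 100 x 78 = 7,800.

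These are upper figures. They assume full follow-up and attendance, and the SAP (Randomization) reports 121 participants randomised. They describe how many sessions lack a scheduled record, not how many events were missed; no dyspnea rate is given from which to compute that.

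**The case against.** The case on the other side has real content.

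- **Dyspnea is not invisible to the DSMB.** Safety concerns are recorded, the medical monitor reviews events, reported adverse events are listed, serious events are weighed against SC, and the board can be asked to review any event bearing on safety. This stands. A reader might infer that the DSMB could not compare dyspnea at all; the documents support only the narrower statement about systematically collected per-session rates.
- **Tracking blood pressure and heart rate is not odd.** Risk from Exercise Training Intervention lists changes in both in the same sentence as shortness of breath. This stands: collecting hypertension and elevated heart rate is a reasonable precaution. The inconsistency lies only in omitting dyspnea.
- **SC reporting is not shown to be absent.** A reader might infer that spontaneous reports would arise almost only beside exercising patients. The documents do not say so. The research assistant's safety role is described in relation to the intervention arms, but Minimization of Risks also has clinicians and dialysis staff helping to monitor participants during dialysis. Unequal ascertainment is possible but not established.
- **Cramping is a weak benchmark.** It is noted only when the participant mentions it. This stands, and it limits how good a dyspnea rate collected in the same way would be. Cramping still has a scheduled place on the record in each session, and dyspnea does not.
- **Some excess is expected.** Exercise at the planned exertion brings breathlessness, so a higher rate than in SC is no surprise. That bears on how the rate is interpreted. A common symptom is also one for which isolated case reports say least.
- **The plan never promises to tabulate every listed risk.** True: boredom and frustration from CT are not session items either. The point is therefore an unexplained gap in safety monitoring, and no commitment is broken.

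**Conclusion.** The point holds in its limited form. Dyspnea is one of three main ET risks in the plan's own list, and the only one with no component among the every-session DSMB items. Under the plan as written, the DSMB may see individual cases but has no scheduled per-session rate by arm. The gap covers the two exercising arms, half of the participants by design. Its consequence in events is unknown.

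The conclusion rests on the public text: a session form or DSMB table template outside these documents might contain a dyspnea item, and that would close the gap. The primary efficacy analysis is not affected. This is an inexpensive improvement that should be made, not a flaw that invalidates the safety monitoring.

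**What to change.** Reconcile the risk lists with Table 2 and with the DSMB data collection paragraph:

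1. Add dyspnea/shortness of breath to the every-session self-report row that already holds cramping and headache, recorded in the same way in all four arms.
2. Show its rate per session by arm in the planned DSMB tables.
3. Leave any pausing limit to the sponsor and the DSMB; none is proposed here.

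The cost is one more item per session on a record that already exists, and one more line in the DSMB table. If the item is noted only when volunteered, as cramping is, no extra contact is needed, but under-reporting remains possible. If staff ask about it, the SC arm at planned size would need about 50 x 52 = 2,600 to 50 x 78 = 3,900 brief contacts. Either way, the rate needs clinical interpretation because some excess during exercise is expected.

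The SAP (Study Design) records that the trial was terminated, so collection in this trial can no longer be changed. Its reports should state that dyspnea was not a scheduled every-session item under the plan, so that few listed cases are not read as reassurance. The amended Table 2 would serve any reuse of the protocol.
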